Pembrolizumab is a humanized monoclonal antibody that blocks the interaction between PD-1 and its ligands, PD-L1 and PD-L2. In a large international Phase 1 clinical trial, pembrolizumab was given to 495 patients with advanced NSCLC to evaluate safety, side-effect profile, and antitumor activity (Garon-2015). Patients (some of whom had received previous therapy and some of whom had not) were treated with various doses and regimens of pembrolizumab. Pembrolizumab had an acceptable side-effect profile and showed anti-tumor activity. Among all patients, the objective response rate was 19.4%, and the median duration of response was 12.5 months. The median duration of progression-free survival was 3.7 months, and the median duration of overall survival was 12.0 months. Keytruda[®] (pembrolizumab) was approved by the FDA in October 2015 for the treatment of patients with metastatic squamous or non-squamous NSCLC with progression on or after platinum-based chemotherapy. Despite these advances, most patients with advanced NSCLC have incurable disease, and additional, effective treatment options are needed. More recently, a trial of pembrolizumab, demonstrated an advantage of pembrolizumab over standard chemotherapy in patients with untreated, advanced NSCLC characterized by $\geq 50\%$ tumor PD-L1 expression. Improvement was reported across multiple efficacy endpoints including survival along with a favorable safety profile (Reck-2016), leading to the approval of pembrolizumab in the first-line treatment setting in this patient population in the US.

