3.2 Phase 2 Study

Following completion of the lead-in dose escalation evaluation, enrollment into the Phase 2 study will proceed.

The treatment arms included in this study are the following:

- 1. Glesatinib plus nivolumab.
- 2. Sitravatinib plus nivolumab.
- 3. Mocetinostat plus nivolumab.

For patients who have experienced progression of disease on or after treatment with a checkpoint inhibitor (CIT-experienced), enrollment into each treatment arm will be stratified by prior outcome of treatment with a checkpoint inhibitor:

- a. Clinical benefit (i.e., RECIST defined partial or complete response or stable disease for at least 12 weeks [-2 week window permitted for radiograph scheduling]) followed by radiographic progression of disease.
- b. No prior clinical benefit (i.e., radiographic progression of disease ≤ 12 weeks after initiation of treatment [+2 week window permitted for radiograph scheduling]).

Thus, the study will include 6 parallel evaluations of clinical activity of nivolumab combination regimens (Figure 3) in patients with prior treatment with a checkpoint

inhibitor. Patients enrolled in the lead-in dose escalation evaluation and receiving the dose of investigational study treatment chosen for the Phase 2 study will be included in the analysis of the Phase 2 endpoints. Patients who discontinue the study prior to the first on-study disease assessment for reasons other than disease progression may be replaced.

For patients without prior checkpoint inhibitor therapy (CIT-naïve), each investigational study treatment arm (i.e., glesatinib, sitravatinib, and mocetinostat) will be stratified according to PD-L1 status:

- a. Having tumor with no/low PD-L1 expression.
- b. Having tumor with high PD-L1 expression.

Tumor PD-L1 expression will be determined by the PD-L1 (28-8) companion diagnostics assay completed through the central laboratory. No/low PD-L1 expression is defined as positivity < 5% of tumor cells; high PD-L1 expression is defined as positivity $\ge 5\%$ of tumor cells. Tumor samples used to establish PD-L1 expression for eligibility must have been collected after the most recent systemic therapy.

Thus, the study will include 6 parallel evaluations of clinical activity of nivolumab combination regimens (Figure 3) in patients without prior treatment with a checkpoint inhibitor.

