Disease response and progression as documented by the Investigator in the Case Report Form (CRF) will be the basis for patient management and study expansion decision making. Unconfirmed objective responses recorded in the CRF may be used as the initial basis for expansion of study enrollment; however, follow-up evaluations on patients with unconfirmed responses must continue to support the decision to continue to the full number of patients to be included in the next stage. Disease assessments will be performed until objective disease progression is documented or subsequent anti-cancer therapy is begun. Central radiology review for disease response and progression may be added to the study during Stage 2. If this occurs, central review of all radiologic assessments performed in the study will be expected (including retrospective review of patients enrolled in Stage 1), and central radiology review for disease response will be the basis for the primary statistical analyses to estimate the objective response rate and its confidence interval, as well as the duration of response and PFS.

Statistical Design Applied to CIT-Experienced and CIT-Naïve with No/Low PD-L1 Expression

This Phase 2 study will use a Predictive Probability Design (Lee-2008) in each treatment arm and strata. In creating the statistical designs, the Type 1 error (α) is constrained to <0.05 and Power (1- β) is constrained to \geq 0.90.

The ORR using nivolumab in the population with advanced non-squamous NSCLC having prior disease progression on a checkpoint inhibitor or patients with non-squamous NSCLC without prior checkpoint inhibitor therapy with no/low PD-L1 expression is

assumed to be 5% (p₀); thus this rate is considered uninteresting. The target ORR using the investigational agents in combination with nivolumab in this study is 30% (p₁). Stage 1 of enrollment will include a minimum of 9 evaluable patients in each treatment strata. With exactly 9 evaluable patients at Stage 1, if at least 1 patient has an Objective Response, 8 additional evaluable patients will be enrolled in the treatment stratum, for a total sample size of 17 evaluable patients. If at least 3 Objective Responses are observed in a treatment stratum, further investigation may be warranted. If the true ORR is 5% (null hypothesis), the probability of early termination during the study is 0.63; the Type 1 error is equal to 0.0466 and the power is equal to 0.9045.

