Statistical Design Applied to CIT-Naïve with High PD-L1 Expression

The ORR using nivolumab in the population with non-squamous NSCLC having high PD-L1 expression is assumed to be 27% (p_0); thus this rate is considered uninteresting. The target ORR using the investigational agents in combination with nivolumab is 50% (p_1).

Stage 1 of enrollment will include approximately 17 evaluable patients. With exactly 17 evaluable patients at Stage 1, if at least 5 patients have Objective Responses, 27 additional evaluable patients will be enrolled, for a total sample size of 44 evaluable patients. If at least 18 Objective Responses are observed, further investigation may be warranted. If the true ORR is 27% (null hypothesis), the probability of early termination during the study is 0.50; the Type 1 error is equal to 0.0303 and the power is equal to 0.9018.

The exact stopping rules for all cohorts will be calculated based on the Predictive Probability Design, once the exact number of patients evaluable at Stage 1 is known. The aim is to get a minimum of 9 evaluable patients at Stage 1 for CIT-experienced and CIT-naïve with no/low PD-L1 expression cohorts and a minimum of 17 evaluable patients at Stage 1 for CIT-naïve with high PD-L1 expression cohort.

In order to be part of the clinical activity evaluable population, the patient must have at least one on-study disease assessment or discontinue from treatment for progressive disease prior to this assessment. Patients who discontinue treatment prior to the first on-study disease assessment for an AE, toxicity, or withdraw consent are considered non-evaluable for disease assessment. These patients will not be part of the clinical activity evaluable population.

[figure not shown]
Expansion Beyond Stage 2

[figure not shown]
The original protocol provided that if results in any strata were of high interest for efficacy, enrollment might be expanded to as many as 100 patients total in each cohort to narrow the 95% Confidence Interval (CI) around the ORR point estimate. Protocol Amendment 3 (Version 4.0) eliminates enrollment expansion beyond Stage 2 except in the sitravatinib segment of the study enrolling patients with CIT-experience.

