9.3.2 Clinical Activity Evaluable Population

In order to be considered eligible for the clinical activity evaluable population, the patient must have at least one on-study disease assessment or discontinue from treatment for progressive disease. Patients who discontinue treatment prior to the first on-study disease assessment for an AE, toxicity, or withdraw consent are considered non-evaluable for disease assessment and will not be part of the clinical activity evaluable population.

This population will be used to present tumor responses as well as to make decision on the Predictive Probability design.

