Potential exists for individual tumor lesions to develop necrosis, to cavitate, have a flare response to treatment or become otherwise difficult to evaluate for a period of time as the result of beneficial study treatment impact. For example, tumor necrosis, cavitation or flare may result in increase in overall size of individual lesions or unclear tumor margins prior to recovery to smaller lesions, development of scar tissue, or complete resolution. The true tumor measurements of lesions should be recorded but the conclusion of progressive disease may be suspended until continued assessment clarifies the nature of the tumor change. If repeat assessments indicate progression of disease, then PD should be recorded on the date of the first assessment giving the impression of progression. If repeat assessments indicate that the change was a process of transition, then NE (not evaluable) should be recorded during the period of transition, and PR or CR may be recorded for subsequent evaluations. The CRF will collect information on the observations during the period of transition to support the assessment conclusions.

Supplemental Investigations

If CR determination depends on a residual lesion that decreased in size but did not disappear completely, it is recommended the residual lesion be investigated with biopsy or fine needle aspirate. If no disease is identified, objective status is CR.

Best Objective Response

Target Lesions	Non-Target Lesions	New Lesion	Point in Time Response	Best Response
CR	CR	No	CR	CR and PR require
CR	Non-CR/Non-PD	No	PR	confirmation at least 4 weeks after first
PR	Non-PD	No	PR	observation
SD	Non-PD	No	SD	SD requires an on-study assessment after at least 6weeks on treatment. Unconfirmed PR or CR are reported as SD.
PD	Any	Yes or No	PD	
Any	PD	Yes or No	PD	
Any	Any	Yes	PD	

Patientive Progression

Patients requiring discontinuation of treatment due to worsening health status attributable to advancement of the malignancy under study but without objective evidence of disease progression should not be reported as PD on tumor assessment CRFs. This should be indicated on the end of treatment CRF as off treatment due to Global Deterioration of Health Status.

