10.0 Interim Analyses

There are no formal interim analyses in the study. Tumor responses will be reviewed for the CAE population to make decisions per the Predictive Probability Design on whether a cohort should be stopped for lack of tumor response as detailed in Section 6.2.

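### Deaths and clinical progression before the first scan have no settled place in the evaluable population, and SAP 7.3 drops them: CAE rates are inflated, and the stage rules may exceed their Type 1 error

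*Protocol*

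**What the plan says.** **Who is evaluable.** Protocol 3.2 says that, to be evaluable, "the patient must have at least one on-study disease assessment or discontinue from treatment for progressive disease prior to this assessment". Section 9.3.2 repeats the rule. Both name AE, toxicity and withdrawn consent before the first assessment as non-evaluable. Neither mentions death or global deterioration.

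**How progression is recorded.** Appendix 4 says that patients taken off treatment because the cancer is making them worse, but "without objective evidence of disease progression should not be reported as PD on tumor assessment CRFs". The end-of-treatment form is to show global deterioration instead. Protocol 6.5 lists objective progression, global deterioration and death as separate reasons for stopping.

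**Replacement.** Protocol 3.2: "Patients who discontinue the study prior to the first on-study disease assessment for reasons other than disease progression may be replaced".

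**The SAP.** Section 4.1.3 says the CAE definition keeps discontinuation for PD as an alternative to an assessment, and points to 7.3 for the text. Section 7.3 has no such alternative: it requires a tumor assessment after baseline.

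**Which population drives the stages.** Protocol 9.3.1 assigns expansion decisions to the mITT population. Protocol 9.3.2 says of the evaluable population: "This population will be used to present tumor responses as well as to make decision on the Predictive Probability design". SAP 10.0 agrees with 9.3.2: "Tumor responses will be reviewed for the CAE population to make decisions per the Predictive Probability Design". SAP 7.2, which renames mITT as the FAS, does not carry over the expansion role.

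**Final analysis.** SAP 11.1.6.1 tests ORR against 5% and 27% in the FAS and scores unassessable patients as non-responders. ORR and CBR are also presented in the CAE population.

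**The concern.** A patient who dies or deteriorates from the cancer before the first scan cannot be a responder. Protocol 3.2 appears to recognize this by admitting early progressors without an assessment. SAP 7.3 removes that route. Under the protocol the route depends on a reason, progressive disease, that Appendix 4 and 6.5 keep apart from unscanned clinical progression and from death.

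Dropping certain non-responders raises any response or benefit rate computed on those who remain. It can also make the stage rules easier to pass when the combination adds nothing. The plan limits Type 1 error to below 0.05 for these rules, and the 9/17 design starts close to that limit, at 0.0466.

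**Working it through.** **1. Classification before the first on-study assessment**

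| Patient | Protocol 3.2 / 9.3.2 | SAP 4.1.3 | SAP 7.3 |
|---|---|---|---|
| Objective PD on an unscheduled scan | in (the scan is an assessment) | in | in |
| Stops for clinical progression, no scan | unclear: in if this counts as stopping for PD; Appendix 4 and 6.5 code it otherwise | unclear, same reason | out |
| Dies, no scan | not named | not named | out |
| Stops for AE, toxicity or consent, no scan | out, by name | out | out |

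Only the middle two rows are in dispute. Under SAP 7.3 the answer is explicit.

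**2. The plan's own figures**

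The inputs are in protocol 3.2. For CIT-experienced and CIT-naïve no/low PD-L1 strata, the null ORR is "assumed to be 5"%. Stage 1 has 9 evaluable patients and continues with at least 1 response; success is at least 3 of 17. For high PD-L1 the null is 27%, Stage 1 has 17 patients and needs 5 responses, and success is at least 18 of 44.

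Type 1 error = Σ over x ≥ r1 of P(X1 = x) × P(X2 ≥ r − x), where X1 and X2 are binomial with the null rate.

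For 9/17 at 5%:
- P(X1 = 0) = 0.95^9 = 0.6302, the stated early termination probability of 0.63.
- P(X1 = 1) = 0.2985, P(X1 = 2) = 0.0629, P(X1 ≥ 3) = 0.0084.
- In the next 8 patients, P(X2 ≥ 2) = 0.0572 and P(X2 ≥ 1) = 0.3366.
- Sum: 0.2985 × 0.0572 + 0.0629 × 0.3366 + 0.0084 = 0.0466, as stated.

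The same formula gives 0.0303 for 17/44, as stated. Power also reproduces (0.9045 and 0.9018).

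**3. Effect of dropping and replacing**

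Let d be the share of treated patients dropped in this way, all non-responders and all replaced. If p0 is the rate among all treated patients, the rate among evaluable patients is p0/(1 − d). At d = 10% this is 0.05/0.90 = 5.6% and 0.27/0.90 = 30%. The documents give no d, so a range is shown.

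| d (assumed) | Type 1 error, 9/17 | Type 1 error, 17/44 |
|---|---|---|
| 0 | 0.0466 | 0.0303 |
| 5% | 0.0529 | 0.0487 |
| 10% | 0.0604 | 0.0778 |
| 15% | 0.0693 | 0.1228 |
| 20% | 0.0801 | 0.1904 |

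The 0.05 limit is passed at d of about 2.8% (9/17) and 5.3% (17/44). At d = 10%, early termination under the null falls from 0.630 to 0.598 and from 0.498 to 0.389.

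**4. CAE rates**

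A never-assessed patient can be neither a responder nor a stable-disease case, so dropping a share d multiplies both ORR and CBR by 1/(1 − d). At d = 10%, a rate of 20% reads as 20/0.90 = 22.2%. This step needs no assumption about replacement or about the scale of the nulls.

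**5. Is 10% a plausible d?**

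The only anchor in the documents is the pembrolizumab Phase 1 study in protocol 1.1.1, where "the median duration of overall survival was 12.0 months". With an assumed constant hazard, deaths by the 8-week scan are 1 − exp(−ln 2 × (56/30.4375)/12.0) = 10.1%, or 8.4% to 11.8% across the ±10-day window. That is a different drug in patients with and without prior therapy, so it is an illustration only. Clinical deterioration without death would add to it.

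**The case against.** A reader might infer that early deaths and clinical progressors cannot enter the evaluable population at all, and that the stage rules do run above their stated Type 1 error. The documents do not support either as a flat statement.

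- **Cannot enter** is literal only under SAP 7.3. In the protocol it is an inference. Appendix 4 governs what is written on forms and does not define evaluability, and the closing words of the 3.2 rule suggest it was meant for patients who progress before a scan. Against that, 3.2 bases expansion decisions on progression as the investigator records it in the CRF, so the coding does feed the rule. A conflict stands; a proven exclusion does not.
- **The evaluable population may not be in charge.** If mITT drives the decision, as 9.3.1 says, and unassessed patients count as non-responders, there is no inflation. The stage rules, however, count evaluable patients throughout, and 9.3.2 and SAP 10.0 name that population.
- **The scale of the nulls is not stated.** If 5% and 27% are rates among evaluable patients, 0.0466 and 0.0303 are correct as they stand. SAP 11.1.6.1 does use the same values in the FAS, which favors the treated scale without settling it.
- **Replacement is permitted, not required**, and not for disease progression. A death from cancer arguably could not be replaced. With a fixed number of treated patients and unchanged thresholds, dropping non-responders would not change the response count.
- **Few decisions may remain.** SAP 4.1.1 and 4.1.2 report that glesatinib stopped and mocetinostat never opened. The sitravatinib CIT-experienced expansion was set on June 2018 results. The documents identify no open stage decision.

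These points make the Type 1 error claim conditional. They do not touch the contradiction between SAP 4.1.3 and 7.3, or the inflation of the CAE rates.

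**Conclusion.** The plan intends patients who stop for progression before the first scan to be evaluable. SAP 7.3 excludes them, and the protocol leaves unscanned clinical progression and early death unclassified. It also gives two answers on which population decides the stages.

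If the CAE population is used as SAP 7.3 defines it, CAE ORR and CBR are overstated by a factor of 1/(1 − d). The stage rules exceed their stated Type 1 error under three further conditions: the CAE population drives the decision, the dropped patients are replaced, and the nulls are treated-population rates. At an assumed 10% loss the values are then 0.060 and 0.078, and the plan's limit is passed at about 2.8% and 5.3% loss.

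The primary ORR in the FAS is unaffected. The SAP already treats such patients as failures elsewhere: 11.1.6.2.3 scores a never-assessed patient who dies by Study Day 122 as a PFS event. This is worth correcting in the final SAP, which SAP 4.0 places before database lock.

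**What to change.** 1. In protocol 3.2 and 9.3.2 and SAP 7.3 (aligned with 4.1.3), state that a patient treated with both drugs who, before the first on-study assessment, dies or stops treatment for progression or global deterioration is evaluable, counts as a non-responder and is not replaced.
2. State which rule takes precedence when a patient stops for an AE and then dies before the first scan. Otherwise the same patient is both non-evaluable and a counted non-responder. Protocol 8.3.1 makes the overlap likely, since fatal progression within the safety reporting period is itself an SAE.
3. Reconcile protocol 9.3.1 with 9.3.2 and SAP 10.0 so that one population drives the Predictive Probability decision.
4. Apply the definition to CAE ORR and CBR and to any stage decision still open.
5. Note that the stated Type 1 error applies to evaluable patients. The remaining AE, toxicity and consent exclusions act in the same direction, so step 1 does not fully restore the stated values on the treated scale.

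The cost is wording in three protocol sections and the matching SAP sections. No new data are needed: reasons for stopping treatment and deaths are already collected. The downside is that go thresholds become slightly harder to reach and the CAE ORR slightly lower.

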4 PATIENT SELECTION AND ENROLLMENT

Patient eligibility must be reviewed and documented by an appropriately qualified member of the Investigator's study team before patients are included in the study. No exceptions to the patient eligibility requirements will be granted by the Sponsor.

4.1 Inclusion Criteria

Patients must meet all of the following inclusion criteria as applicable for phase of the study to be eligible for enrollment into the study:

- 1. Histologically confirmed non-squamous NSCLC with metastatic or unresectable, locally advanced disease, not amenable to treatment with curative intent.
- 2. Receipt of at least one prior treatment in the advanced disease setting.
 - a) CIT-experienced: Most recent treatment must have included a checkpoint inhibitor (i.e., anti-PD-1 or anti-PD-L1 including nivolumab, pembrolizumab, durvalumab, atezolizumab or avelumab) with the result of progression of disease on or after treatment.

Note: For the PK sub-studies as outlined within Appendix 5 and Appendix 6, treatment with a checkpoint inhibitor (i.e., anti-PD-1 or anti-PD-L1) does not need to be included in the most recent treatment.

- b) CIT-naïve: Receipt of prior platinum-based doublet chemotherapy.
- 3. CIT-naïve: Molecular analysis of tumor sample collected following most recent therapy, assessed using the PD-L1 (28-8) CDx assay. Inclusion in the treatment arm will be based on documented no/low PD-L1 expression (positivity < 5% of tumor cells) or high PD-L1 expression (positivity ≥ 5% of tumor cells). *Note: This criterion does not apply to the PK sub-studies as outlined within Appendix 5 and Appendix 6.*
- 4. Measurable disease as per RECIST version 1.1.
- 5. Eastern Cooperative Oncology Group (ECOG) performance status 0, 1 or 2 (Appendix 1).
- 6. Adequate bone marrow and organ function demonstrated by:
 - Absolute neutrophil count $\geq 1,000/\text{mm}^3 \ (\geq 1.0 \times 10^9/\text{L})$
 - Platelet count $\ge 50 \times 10^9 / L \ (> 50,000 \text{ per mm}^3)$

- Alanine aminotransferase (ALT) and aspartate aminotransferase (AST)
 ≤ 2.5 × Upper Limit of Normal (ULN), or ≤ 5.0 × ULN for patients with documented liver metastases.
- Serum bilirubin $\leq 1.5 \times \text{ULN}$ or $\leq 3.0 \times \text{ULN}$ for patients with Gilbert Syndrome or documented liver metastases.
- Serum creatinine $\leq 1.5 \times ULN$.
- 7. \geq 18 years of age.
- 8. Women of child-bearing potential (WOCBP) or men whose partner is a WOCBP agrees to use contraception while participating in this study, and for a period of 6 months following termination of study treatment.
- 9. Completed informed consent process, including signing IRB/EC-approved informed consent form.
- 10. Willing to comply with clinical trial instructions and requirements.

